3.2 Sample Size

This study is to provide clinical experience with evolocumab in approximately 150 pediatric subjects, compared to the current experience described in the Protocol [Sections 2.3](#) and [Section 2.4](#). Based on the treatment effect from the global phase 3 study in adult subjects with HeFH, evolocumab reduced LDL-C by approximately 55%. A planned total sample size of 150 pediatric subjects (100 randomized to evolocumab 420 mg QM and 50 randomized to placebo QM) will provide approximately 99% power in testing the superiority of evolocumab 420 mg QM over placebo. The sample size calculation is performed using a two-sided t-test with a 0.05 significance level, assuming a treatment effect of 40% reduction in LDL-C, a common standard deviation (SD) of 20%, and 20% of subjects discontinuing investigational product prior to completion of the study.

The power calculation is derived using nQuery version 7.01.

4. Study Endpoints and Covariates

4.1 Study Endpoints

4.1.1 Primary Efficacy Endpoint

- Percent change from baseline to week 24 in LDL-C

4.1.2 Secondary Efficacy Endpoints

[figure not shown]
- Mean percent change from baseline to weeks 22 and 24 in LDL-C¹
- Change from baseline to week 24 in LDL-C²
- Percent change from baseline to week 24 in the following³:
 - non-HDL-C
 - ApoB
 - total cholesterol/HDL-C ratio
 - ApoB/ApoA1 ratio

[figure not shown]
^{1,2,3} See [section 10.1](#) for detail on multiplicity adjustment

4.1.3 Tertiary Efficacy Endpoints

- Percent change from baseline to week 24 in the following:
 - total cholesterol
 - VLDL-C
 - HDL-C
 - ApoA1
 - Triglycerides
 - Lp(a)
- Mean percent change from baseline to weeks 22 and 24 in the following:
 - non-HDL-C
 - ApoB
 - total cholesterol/HDL-C ratio
 - ApoB/ApoA1 ratio
 - total cholesterol
 - VLDL-C
 - HDL-C
 - ApoA1
 - triglycerides
 - Lp(a)

4.1.4 Exploratory Endpoints

4.1.5 Secondary Safety Endpoints

- Subject incidence of treatment emergent adverse events
- Safety laboratory values and vital signs at each scheduled assessment
- Incidence of anti-evolocumab antibody (binding and neutralizing) formation

4.1.6 Secondary Pharmacokinetics Endpoints

- Serum concentration of evolocumab at each scheduled assessment

4.1.7 Other Safety Endpoints

- Change from baseline score in the components of the Cogstate battery at each scheduled administration

4.2 Planned Covariates

Stratification factors

- Screening LDL-C (< 160 mg/dL [4.1 mmol/L], ≥ 160 mg/dL)
- Age (< 14 years, ≥ 14 years)

Baseline characteristics

- Gender
- Race (black, white, and other)
- Region (North America, Europe, other)
- LDL-C (< baseline median, ≥ baseline median)
- Glucose tolerance status (type 2 diabetes mellitus, metabolic syndrome, neither type 2 diabetes mellitus nor metabolic syndrome)

- Lipid modifying background therapy (statin intensity defined based on modified ACC/AHA guidance, see [Appendix C](#))

5. Hypotheses and/or Estimations

The primary hypothesis of the primary endpoint is: the null hypothesis is that there is no difference in the mean percent change from baseline at week 24 in LDL-C between

evolocumab and placebo, when added to standard of care, and the alternative hypothesis is that a mean difference does exist.

6. Definitions

6.1 Study Time Points

Enrollment Date

Enrollment Date is defined as the date collected on the eCRF.

Randomization date

Randomization date is defined as the date subject was allocated to a treatment group.

Study Day 1

For each subject, Study Day 1 is defined as the first day of investigational product (IP) administration.

Study Day

For each subject, and for a given date of interest, study day is defined as the number of days since Study Day 1:

Study day = (date of interest – Study Day 1 date) + 1.

If the date of interest is prior to the Study Day 1:

Study day = (date of interest – Study Day 1 date), so that the day prior to Study Day 1 is study day - 1.

First Dose Date of Investigational Product

For each subject, the First Dose Date of Investigational Product is defined as the date of the first administration of IP as recorded on the IP administration eCRF, equivalent to study day 1.

Last Dose Date of Investigational Product

For each subject, the Last Dose Date of Investigational Product is defined as the date of the last administration of IP.

End of Study (EOS) Date

End of study for each subject is defined as the date the subject last completed a protocol-specified procedure. The date will be recorded on the End of Study CRF page.

Study End Date

The Study End Date is the last EOS date of all randomized subjects.

6.2 Demographics and Baseline Related Definitions

Age

Age at randomization will be derived in years in the clinical database.

Baseline Lipid and Lipid-related Parameters

Baseline values for fasting lipids (total cholesterol, HDL-C, LDL-C, VLDL-C and triglycerides), ApoA1, ApoB, hsCRP, Lp(a) and their derived parameters (eg, ratio between them) are defined as the mean of the two most recent non-missing fasting concentrations measured through central lab prior to or on Study Day 1. If for any reason only 1 value is available, then that value will be used as baseline.

BMI

Subject's BMI will be derived in kg/m² in the clinical database.

Other Baseline Values

For ECG, the baseline value is defined as the mean over all non-missing triplicate averages of 3 (or all available) readings from each set of triplicate taken prior to or on Study Day 1.

For ██████ the baseline value is defined as the average of the last two non-missing values collected prior to first IP administration. If for any reason only 1 value is available, then that value will be used as baseline.

For cIMT, the baseline value is defined as the non-missing value collected on or prior to study day 28.

For all other variables, the baseline value is defined as the last non-missing value collected prior to or on Study Day 1.

Change (absolute change) from Baseline

The arithmetic difference between a post-baseline value and baseline for a given time point:

Change (absolute change) from baseline = (post-baseline value – baseline value)

Percent Change from Baseline

The percent change from baseline for a given variable at a given time point is defined as:

100 x [(value at given time point – baseline value) / baseline value]

Baseline Metabolic Syndrome

For each subject without type 2 diabetes mellitus, metabolic syndrome is identified by the presence of 3 or more of the components listed below (modified AHA/NHLBI criteria, [Fryar et al 2012](#), [Ji et al 2010](#)). Subjects with type II diabetes cannot be categorized as having metabolic syndrome.

Age 10 to <16 years

Risk Factor	Defining Level
Elevated waist circumference:	Obesity \geq 90 percentile or adult cut-off if lower (refer to the cut-offs below)
Non-Asian (Fryar et al., 2012):	
Male:	
Age 10	\geq 85.6 cm
Age 11	\geq 90.4 cm
Age 12	\geq 93.7 cm
Age 13	\geq 96.7 cm
Age 14	\geq 101.3 cm
Age 15	\geq 99.9 cm
Female:	
Age 10	\geq 84.1 cm
Age 11	\geq 88 cm
Age 12	\geq 88 cm
Age 13	\geq 88 cm
Age 14	\geq 88 cm
Age 15	\geq 88 cm
Asian (Ji et al, 2010):	
Male:	
Age 10	\geq 73.1 cm
Age 11	\geq 75.6 cm
Age 12	\geq 77.4 cm
Age 13	\geq 78.6 cm
Age 14	\geq 79.6 cm
Age 15	\geq 80.5 cm
Female:	
Age 10	\geq 67.8 cm
Age 11	\geq 70.4 cm
Age 12	\geq 72.6 cm
Age 13	\geq 74.0 cm
Age 14	\geq 74.9 cm
Age 15	\geq 75.5 cm
Triglycerides	\geq 1.7 mmol/L (150 mg/dL)

HDL cholesterol	<1.03 mmol/L (40 mg/dL)
Blood pressure	SBP ≥ 130 mmHg or DBP ≥ 85 mmHg OR Hypertension checked 'yes' on CV Medical History eCRF
Fasting glucose	≥ 5.6 mmol/L (100 mg/dL)

For Age ≥16 years

Risk Factor	Defining Level
Elevated waist circumference:	
Non-Asian:	
Male	≥ 102 cm
Female	≥ 88 cm
Asian:	
Male	≥ 90 cm
Female	≥ 80 cm
Triglycerides	≥ 1.7 mmol/L (150 mg/dL)
HDL cholesterol	
Male	<1.03 mmol/L (40 mg/dL)
Female	< 1.29 mmol/L (50 mg/dL)
Blood pressure	SBP ≥ 130 mmHg or DBP ≥ 85 mmHg OR Hypertension checked 'yes' on CV Medical History eCRF
Fasting glucose	≥ 5.6 mmol/L (100 mg/dL)

Baseline CHD Risk Factors

A subject will be categorized as having 2 or more CHD Risk Factors (Y/N) from the list of the modified NCEP ATP III risk factors:

- current cigarette smoking
- hypertension
- type II diabetes mellitus
- family history of premature CHD as recorded on the eCRF
- low HDL-C defined as baseline HDL-C < 40 mg/dL for both males and females with age 10 to < 16 years; < 40 mg/dL in male and < 50 mg/dL in female with age ≥ 16 years.

6.3 Other Study Related Definitions

Analytical Study Week Assignments

Analytical windows will be used to assign parameter measurements to study weeks. The algorithm is provided in [Appendix A](#).

Actual Treatment Group

A subject's actual treatment group is the randomized treatment group, unless the subject receives treatment throughout the study that is different than the randomized treatment group assignment, in which case the actual treatment group is the treatment received.

Investigational Product (IP)

Evolocumab SC 420 mg QM and placebo SC QM.

Study Exposure Period in Months

For each randomized subject, Study Exposure Period = (EOS date – Enrollment Date + 1) / 365.25 * 12

IP Exposure Period in Months

IP Exposure Period = [min (Last IP Dose Date + 28 days, EOS Date) - Study Day 1 + 1] / 365.25 * 12

Treatment-emergent adverse event

Treatment emergent adverse events are events categorized as Adverse Events (AEs) starting on or after first dose of investigational product as determined by “Did event start before first dose of investigational product” equal to No or missing on the Events eCRF and up to and including 30 days after last dose of investigational product or the EOS date, whichever is earlier. Any AE that cannot be defined clearly as a TEAE will be considered a TEAE in the database.

Reflexive Approach for LDL-C and VLDL-C

For all analyses related to LDL-C and VLDL-C, unless specified otherwise, an LDL-C reflexive approach will be used. When calculated LDL-C is less than 40 mg/dL or triglycerides > 400 mg/dL, the UC LDL-C **value from** the same blood sample will be used instead of calculated LDL-C and the UC VLDL-C **value from the same blood sample will be used instead of calculated VLDL-C**, if available.

7. Analysis Subsets

7.1 Full Analysis Set

The full analysis set (FAS) includes all randomized subjects who received at least 1 dose of IP. It will be used for both efficacy and safety analyses. In efficacy analyses,

subjects will be grouped according to their randomized treatment group assignment, regardless of the treatment received. For safety analyses, subjects will be grouped according to their actual treatment group (as defined in [Section 6.3](#)).

7.2 Completer Analysis Set

The completer analysis set (CAS) includes subjects in the FAS who adhered to the scheduled IP and have observed values for the primary endpoints. The completer analysis set will be used in sensitivity analyses of the primary endpoints.

7.3 Subgroup Analyses

Subgroup by stratification factor

- Screening LDL-C (< 160 mg/dL, ≥ 160 mg/dL)
- Age (< 14 years, ≥ 14 years)

Subgroup by baseline characteristics

- Gender
- Race (black, white, and other)
- Region (North America, Europe, other)
- LDL-C ($<$ baseline median, \geq baseline median)
- Glucose tolerance status (type 2 diabetes mellitus, metabolic syndrome, neither type 2 diabetes mellitus nor metabolic syndrome)

- Lipid modifying background therapy (statin intensity defined based on modified ACC/AHA guidance, see [Appendix C](#))

8. Interim Analysis and Early Stopping Guidelines

No interim analysis is planned for this study.

An external independent DMC has been established to formally review the accumulating data from this and other completed and ongoing studies with evolocumab to ensure there is no avoidable increased risk of harm to subjects. The independent DMC is chaired by an external academic cardiologist who is an expert in lipids and clinical trials. Analyses for the DMC are provided by the Independent Biostatistical Group (IBG), which is external to Amgen.

9. Data Screening and Acceptance

9.1 General Principles

The objective of the data screening is to assess the quantity, quality, and statistical characteristics of the data relative to the requirements of the planned analyses.

9.2 Data Handling and Electronic Transfer of Data

The Amgen Global Study Operations – Data Management (GSO-DM) department will provide all data to be used in the planned analyses. This study will use the RAVE database.

All data collected in the eCRF will be extracted from RAVE. Protocol deviations will be transferred from eClinical. Final PK data for all randomized subjects will be transferred from statistical programming to Amgen's PKDM group. Unblinded subject and box ID randomization lists will be provided by Amgen's randomization group and the IVRS when the study stops. Details on data transfer will be provided in the Data Transfer Plan.

9.3 Handling of Missing and Incomplete Data

9.3.1 Patterns of Missing Data

Subjects may be missing specific data points for various reasons. In general, data may be missing due to a subject's early withdrawal from study, a missed visit, or non-evaluability of a data point or an endpoint at a particular point in time. In the Data Quality Review (DQR) process, queries will be made to the sites to distinguish true missing values from other unknown values (e.g. due to measurement or sample processing error). All attempts will be made to capture missing or partial data for this trial prior to the database lock.

The frequency and pattern of missing data for efficacy endpoints will be assessed through descriptive summaries of the measurements over time.

9.3.2 Missing Lipid Measurements

For primary efficacy endpoint, the primary analysis will be performed using repeated measures linear effects model without imputation. **To assess the impact of missing data**, sensitivity analyses will be performed based on multiple imputation (**details in section 10.5.1**).

Imputation will not be performed for other efficacy endpoints.

9.3.3 Handling of Incomplete Dates

Adverse event and concomitant medication with completely or partially missing start dates will be queried. After the issue is queried, if the date is still incomplete with year only or year and month only, the start date will be imputed as described in Table 1 below.

Table 1. Imputation Rules for Incomplete Dates

	Missing	Imputation	Exception
Start date (AE and concomitant medication)	Day	1	Default to Study Day 1 if an event starts the same year and month as Study Day 1
	Day/Month	1-Jan	Default to Study Day 1 if an event started the same year as Day 1

9.4 Detection of Bias

This study has been designed to minimize potential bias by the use of randomization of subjects into treatment groups and the use of blinding. Other factors that may bias the results of the study include:

- major protocol deviations likely to impact the analysis and interpretation of the efficacy endpoints
- subject level unblinding before final database lock and formal unblinding
- DMC related analyses

Important protocol deviations likely to impact the analysis and interpretation of the efficacy endpoints will be tabulated in the Clinical Study Report (CSR).

Any unblinding of individual subjects prior to formal unblinding of the study will be documented in the CSR. The impact of such unblinding on the results observed will be assessed.

For DMC related analyses, details of access to subject level treatment assignments are provided in the protocol, Section 10.3.

Additional sensitivity analyses may be included to assess the impact of potential biases on the primary endpoint. If any sensitivity analyses are required to evaluate potential biases in the study's conclusions, then the sources of the potential biases and results of the sensitivity analyses will be documented in the CSR.

9.5 Outliers

Various methods, including univariate summaries, histograms, scatter plots, box plots, and line graphs, may be used to identify outliers in key safety and efficacy variables. Extreme data points will be identified during the blinded review of the data prior to database lock. Such data points will be reviewed with clinical data management to ensure accuracy. The primary analyses will include outliers in the data. Sensitivity analyses may be undertaken if extreme outliers for a variable are observed.

9.6 Distributional Characteristics

Distributional assumptions for the primary and secondary endpoints will be assessed. If the assumptions are not met, then alternative methods will be utilized. The use of alternative methods will be fully justified in the CSR.

9.7 Validation of Statistical Analyses

Programs will be developed and maintained, and output will be verified in accordance with current risk-based quality control procedures.

Tables, figures, and listings will be produced with validated standard macro programs where standard macros can produce the specified outputs.

The production environment for statistical analyses consists of Amgen-supported versions of statistical analysis software; for example, the SAS System version 9.3 or later.

10. Statistical Methods of Analysis

10.1 General Principles

The final analysis will be conducted when all subjects have either completed all the scheduled study visits or have early terminated from the study. At that time, the database will be cleaned, processed and a snapshot will be taken; the study will also be unblinded. Based on the snapshot, efficacy and safety analyses will be performed on the FAS. Unless specified otherwise, the FAS will be the default analysis set in this study and data will be summarized by randomized treatment group. The superiority of evolocumab to placebo will be assessed for all efficacy endpoints.

Subject disposition, demographics, baseline characteristics, and exposure to IP will be summarized.

Summary statistics for continuous variables will include the number of subjects, mean, median, standard deviation or standard error, minimum, and maximum. For categorical variables, the frequency and percentage will be summarized.

Methods of handling missing data for efficacy endpoints will be described throughout this section. Missing data will not be imputed for safety endpoints.

Multiplicity Adjustment Method

In order to preserve the familywise error rate at 0.05, multiplicity adjustment for the multiple endpoints (**primary efficacy endpoint: percent change from baseline to week 24 in LDL-C and secondary efficacy endpoints: mean percent change from**

baseline to weeks 22 and 24 in LDL-C, change from baseline to week 24 in LDL-C and percent change from baseline to week 24 in non-HDL-C, ApoB, total cholesterol/HDL-C ratio and ApoB/ApoA1 ratio) will be performed using sequential gatekeeping and Hochberg procedures (Hochberg, 1988) as follows:

1. If the treatment effect from the primary analysis of the primary endpoint is significant at a significance level of 0.05, statistical testing of the **mean percent change from baseline to weeks 22 and 24 in LDL-C and change from baseline to week 24 in LDL-C** will proceed using the sequential procedure with a significance level of 0.05 (ie, **change from baseline to week 24 in LDL-C** will be tested only if **mean percent change from baseline to weeks 22 and 24 in LDL-C** is statistically significant at 0.05 significance level).
2. If the treatment effect from **change from baseline to week 24 in LDL-C** is significant at a significance level of 0.05, statistical testing of the **percent change from baseline to week 24 in non-HDL-C, ApoB, total cholesterol/HDL-C ratio and ApoB/ApoA1 ratio** will follow the Hochberg procedure at a significance level of 0.05.

Unless specified otherwise, all other hypothesis testing will be 2-sided with a significance level of 0.05.

10.2 Subject Accountability

The number of subjects screened, randomized, receiving IP, and completing the study will be summarized. Key study dates for the first subject enrolled, last subject enrolled and last subject's end of study will be presented.

Study discontinuation and IP discontinuation will be tabulated separately by reasons for discontinuation.

The number and percent of subjects randomized will be tabulated by the stratification factors.

The number of subjects included in and excluded from each analysis set and reason for exclusion will also be summarized.

10.3 Important Protocol Deviations

Important Protocol Deviations (IPDs) categories are defined by the study team before the first subject's visit and updated during the IPD reviews throughout the study prior to

database lock. These definitions of IPD categories, sub-category codes, and descriptions will be used during the course of the study.

Eligibility deviations are defined in the protocol.

10.4 Demographic and Baseline Characteristics

Demographic (ie, **gender, race, region**) and baseline disease characteristics (**cardiovascular medical history, laboratory parameters and lipid-regulating medication**) will be summarized by treatment group and overall using descriptive statistics. If multiple races have been reported for a subject, the subject will be categorized as multiple race.

10.5 Efficacy Analyses

The following table summarizes the key efficacy analyses that will be conducted:

Table 2. Key Efficacy Analyses Summary Table

Endpoint	Statistical Analysis Method	P-values from the Statistical Tests	Hierarchical Testing Procedure for testing of Treatment Effect vs. Placebo. As specified in the Multiplicity Adjustment Method diagram
Primary Endpoint Percent change in LDL-C from baseline to week 24	Repeated measures model	P1= the p-values for the primary endpoint	P1 compare to $\alpha = 0.05$
Secondary Endpoint¹ Mean percent change from baseline at weeks 22 and 24 in LDL-C	Repeated measures model	P2a=the p-values for the secondary endpoint ¹	If $P1 < 0.05$ → P2a will be tested and compare to $\alpha = 0.05$ Else(i.e. primary endpoint is not significant) → No further testing
Secondary Endpoint² Change from baseline to week 24 in LDL-C	Repeated measures model	P2b= the p-values for the secondary endpoint ²	If $P2a < 0.05$ → P2b tested and compare to $\alpha = 0.05$ Else(i.e. secondary endpoint ¹ is not significant) → No further testing

Table 2. Key Efficacy Analyses Summary Table

Endpoint	Statistical Analysis Method	P-values from the Statistical Tests	Hierarchical Testing Procedure for testing of Treatment Effect vs. Placebo. As specified in the Multiplicity Adjustment Method diagram

Secondary Endpoints³ Percent change from baseline to 24 weeks In each of the following lipid parameters:
 
 • non-HDL-C • ApoB • total cholesterol/HDL-C ratio • ApoB/ApoA1 ratio 	Repeated measures model	
For each lipid parameter
 
P2c= p-values for each lipid parameter
	
If P2b < 0.05,
 
→ All P2c's from each lipid parameter will be tested through Hochberg method with $\alpha = 0.05$
 
Else(i.e. secondary endpoint² is not significant)
 
→ No further testing

10.5.1 Analyses of Primary Endpoints

10.5.1.1 Primary Analysis of Primary Efficacy Endpoints

The estimand of primary interest is the difference in mean percent change from baseline in LDL-C at week 24 regardless of treatment adherence for subjects in FAS. A repeated measures linear effects model (Littell et al, 2000) will be used to compare the efficacy of evolocumab with placebo. The repeated measures model will include terms for treatment group, stratification factors (as appropriate), scheduled visit and the interaction of treatment with scheduled visit. To account for the repeated LDL-C measurements within a subject across the visits, the repeated measures linear effects model will use an unstructured covariance. Missing values will not be imputed when the repeated measures linear effects model is used. The analysis will use LDL-C values measured regardless of treatment adherence.

Multiplicity adjustment procedures are defined in [Section 10.1](#).

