Procedures: Subjects being considered for participation in this study, and who have signed informed consent or subject assent, will be assessed for inclusion and exclusion criteria. Medical and medication history will be obtained. Subjects will undergo screening assessments, including a SC administration of placebo to evaluate tolerability of the SC injection via the prefilled AI/pen. Lipid eligibility screening must be conducted after the subject has been on a low-fat diet and receiving lipid lowering therapy that includes an optimal dose of a statin not requiring uptitration in the opinion of the investigator and has been stable for ≥ 4 weeks. Subjects should maintain their diet, lipid-lowering therapy, and exercise regimen unchanged throughout screening and all phases of study participation. Eligible subjects will be randomized to receive IP (evolocumab or placebo), in addition to their background lipid lowering therapy. An interactive voice response system and/or interactive web response system (IVRS/IWRS) will allocate subjects to administration of investigational product. Day 1 is defined as the day of first administration of investigational product. Subsequent study visits are at weeks 4, 12, 20, 22, and 24 (EOS, end-of-study). Day 1 and week 24 visits must be scheduled at approximately the same time of day, and should be performed as close as possible to 8 am as the hormones measured have diurnal variation. IP administration is every 4 weeks. Administration at weeks 8 and 16 can be at

the study site (optional visit) or at a location other than the study site. Last administration of IP is at week 20. Subjects who discontinue IP early for any reason will be asked to continue to return for all other study procedures and measurements until the end of the study.

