- Reductions in LDL-C and improvements in other lipid parameters were reversible upon cessation of treatment, with no evidence of rebound.
- Evolocumab 140 mg Q2W and 420 mg QM dosing regimens were clinically equivalent; no clinically meaningful differences, with respect to reductions in LDL-C and improvements in other lipid parameters, were noted between the 2 doses.
- Evolocumab 140 mg Q2W and 420 mg QM dosing regimens were effective in all subgroups relative to placebo and ezetimibe with no notable differences observed among subgroups (ie, age, race, gender, region, body mass index, current smoking status, baseline CHD risk factors, family history of premature CHD, glucose tolerance status [diabetes mellitus type 2, metabolic syndrome, or neither], hypertension, unbound baseline PCSK9, baseline LDL-C, baseline triglycerides, and [National Cholesterol Education Program \[NCEP\], 2002](#) high risk status).
- Administration of evolocumab with the prefilled autoinjector/pen (AI/pen) was shown to be safe and effective for its intended use and the conditions of use, including self-administration in the home-use setting.

The results of the analyses conducted in the primary hyperlipidemia (heterozygous familial and nonfamilial) and mixed dyslipidemia integrated safety analysis set for evolocumab demonstrated the following with respect to safety:

- In the integrated parent studies, the most common ($\geq 2\%$) adverse events in the combined evolocumab group or control group were nasopharyngitis, upper respiratory tract infection, headache, back pain, and myalgia. Common adverse events in the year 1 standard of care (SoC)-controlled period did not include headache and myalgia; otherwise, common adverse events were the same as integrated parent studies with the addition of arthralgia and hypertension. There were no additional common adverse events during the year 2+ open-label extension (OLE) period.

- The types and incidence of adverse events were consistent across studies where evolocumab was given as monotherapy, in combination therapy with statins (with or without ezetimibe) or in subjects with statin intolerance.
- Most adverse events were grade 1 or 2.
- Serious adverse events, deaths, positively adjudicated clinical events, and adverse events leading to discontinuation of investigational product (IP) were infrequently reported and similar across treatment groups.

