3.1 Study Design

This is a randomized, placebo-controlled, double-blind, parallel group, multicenter study. Subjects are eligible for screening if they are 10 to 17 years of age at time of randomization and have met the local applicable diagnostic criteria for HeFH. Subjects considered for enrollment will undergo screening assessments, including laboratory screening by central laboratory. Approximately 150 eligible subjects will be randomized in a 2:1 ratio to receive 24 weeks of QM evolocumab or placebo. Randomization will be stratified by screening LDL-C (< 160 mg/dL [4.1 mmol/L] vs ≥ 160 mg/dL) and age (< 14 years vs ≥ 14 years) at randomization.

The study includes collection of biomarker development samples. Where permitted by local regulations, subjects will be invited to consent to pharmacogenetic analyses.

Events of death, myocardial infarction (MI), hospitalization for unstable angina, coronary revascularization, stroke, transient ischemic attack (TIA), and hospitalization for heart failure will be adjudicated by an independent Clinical Events Committee (CEC). Subject incidence of exploratory endpoint events will be summarized for each treatment group. Processes of event identification and submission to the CEC are described in a CEC Endpoint Reporting Manual.

An independent data monitoring committee (DMC) will formally review the accumulating data from this and other completed and ongoing studies with evolocumab to ensure

there is no avoidable increased risk for harm to subjects. Analyses for the DMC will be provided by a group which is external to Amgen.

After completion of Study 20120123, subjects will be offered participation in an extension study where they will receive open-label evolocumab.

The overall study design is described by a study schema at the end of the protocol synopsis section.

The study endpoints are defined in [Section 4.1](#)

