10.5.2 Analyses of Secondary Efficacy Endpoints

The statistical model and testing of the secondary efficacy endpoints will be similar to the primary analysis of the primary endpoint.

Multiplicity adjustment procedures are defined in [Section 10.1](#)

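### SAP 10.5.1.1: fitting the unstructured covariance by arm is a cheap, minor improvement, because under 2:1 allocation a shared matrix mis-sizes the week 24 standard error whenever the arm variances differ

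*SAP*

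**What the plan says.** The primary model in SAP 10.5.1.1 has treatment, stratification factors, visit and treatment-by-visit as mean terms, and "the repeated measures linear effects model will use an unstructured covariance". The stated purpose is correlation between a subject's visits. Treatment arm is not mentioned, and no robust standard error or degrees-of-freedom method is named. Protocol 10.5.2 names no covariance structure at all.

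Four other statements bear on whether the two arms will have the same variance:

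- SAP 10.5.1.1: "The analysis will use LDL-C values measured regardless of treatment adherence".
- Protocol Synopsis, Procedures: "Subjects who discontinue IP early for any reason will be asked to continue to return for all other study procedures and measurements".
- Protocol 2.2.2, on the adult programme: "Reductions in LDL-C and improvements in other lipid parameters were reversible upon cessation of treatment, with no evidence of rebound".
- SAP 3.2 sizes the trial at 100 versus 50, "assuming a treatment effect of 40% reduction in LDL-C, a common standard deviation (SD) of 20%, and 20% of subjects discontinuing investigational product".

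SAP 3.1 has subjects "randomized in a 2:1 ratio to receive 24 weeks of QM evolocumab or placebo". SAP 9.6 covers failed assumptions in general terms: "If the assumptions are not met, then alternative methods will be utilized". The sensitivity analyses in SAP 10.5.1.2 are the completer set, the Quade test and multiple imputation. None is an unequal-variance version of the primary model.

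**The concern.** A shared matrix pools the two arms' variances in proportion to their degrees of freedom, so the larger arm dominates. The variance of a difference in means depends more on the smaller arm. With equal allocation the two effects cancel almost exactly, but at 2:1 they do not. If the larger evolocumab arm is the more variable one, the standard error is too large. If placebo is, the standard error is too small.

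The plan itself gives a reason for unequal variances. Evolocumab subjects who stop treatment lose their LDL-C reduction and are still measured and analysed, so that arm becomes a mixture of treated and reverted values. Placebo subjects who stop have no drug effect to lose. At stake are the standard error of the primary effect and any interval built from it.

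**Working it through.** **Inputs.** From SAP 3.2: 100 and 50 subjects, effect 40 points, SD 20, 20% stopping, two-sided 0.05. Assumed, because the documents do not give them: 20 is the SD for placebo and for off-drug values; subjects who stop are all observed and fully back to baseline at week 24; the on-drug SD is 20 unless stated otherwise.

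**The plan's own figure.** SE = 20 × √(1/100 + 1/50) = 3.464, and 40/3.464 = 11.5. Power is above 99.99%, in line with the stated figure of approximately 99%. It remains above 99.99% at 80 versus 40 with the effect diluted to 0.8 × 40 = 32: SE = 20 × √(1/80 + 1/40) = 3.873, and 32/3.873 = 8.3.

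**Formulas.** With treatment-by-visit means and complete data, the week 24 contrast is a two-sample comparison. Let p be the share of evolocumab subjects off drug at week 24, s the on-drug SD and D the effect lost on stopping.

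- Evolocumab variance: V1 = (1 − p)s² + 400p + p(1 − p)D²
- Placebo variance: V0 = 400
- True SE = √(V1/100 + V0/50)
- Shared-matrix SE = √{[(99V1 + 49V0)/148] × 0.03}

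**Results for s = 20, D = 40.** Coverage is for the shared matrix and a nominal 95% interval, from 100,000 simulated trials per row.

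| p | V1 | Shared SE | True SE | Ratio | Coverage |
|---|---|---|---|---|---|
| 0.03 | 446.6 | 3.596 | 3.531 | 1.019 | 95.4% |
| 0.05 | 476 | 3.678 | 3.572 | 1.030 | 95.6% |
| 0.10 | 544 | 3.859 | 3.666 | 1.053 | 96.0% |
| 0.20 | 656 | 4.140 | 3.816 | 1.085 | 96.6% |

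Worked row, p = 0.05: V1 = 400 + 0.05 × 0.95 × 1600 = 476. Shared: (99 × 476 + 49 × 400)/148 = 450.8; 450.8 × 0.03 = 13.53; square root 3.678. True: √(4.76 + 8) = 3.572.

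The p = 0.20 row is the upper bound, because it takes every planned stopper as observed and fully reverted. The mean interval half-width there is 8.17 points shared and 7.54 by arm. If stoppers keep half the effect (D = 20), the excess falls to 0.8%, 1.5% and 2.5% at p = 0.05, 0.10 and 0.20. If 20 is each arm's total SD, V1 = V0 and the ratio is 1.

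**When the SE would be too small.** This needs V1 below 400. Solving V1 = 400 with D = 40 gives a break-even on-drug SD of √(304/0.95) = 17.9 at p = 0.05, √(216/0.90) = 15.5 at p = 0.10 and √(64/0.80) = 8.9 at p = 0.20. For illustration, an assumed on-drug SD of 15 gives a ratio of 0.910 with nobody off drug (coverage 92.6%), 0.958 at p = 0.05 and 1.043 at p = 0.20.

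**By-arm variances.** Two-sample intervals with separate variances covered 94.9% to 95.1% in all these complete-data cases. When the variances are equal the by-arm half-width is 6.86 against 6.83 shared, so almost nothing is lost.

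**Repeated-measures check.** A three-visit unstructured model was simulated with about 20% of week 24 values missing at random, assumed visit correlations of 0.6 to 0.8, and SDs of 25.6 (= √656) and 20. The mean shared SE was 4.421 against an empirical SD of 4.037, a ratio of 1.10. The by-arm SE was 4.07.

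**Unobserved stoppers.** If 20% stop and half of them are missing at week 24, observed cases estimate 40 × 0.80/0.90 = 35.6 against a true 32. Coverage of 32 is then 87% shared and 85% by arm. Neither is adequate, and the cause is bias, not the covariance.

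**The case against.** The strongest reply is that the plan's own figures give no error. It assumes a common SD of 20, and every non-zero result above rests on inputs it does not state. That stands. The documents do not show that the standard error is wrong, only that it is correct when the variances happen to be equal.

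Second, the only mechanism that the documents support makes the larger arm more variable, so a shared matrix is conservative. This also stands. A reader might infer from the 92.6% coverage figure that the primary interval is anti-conservative. That figure needs on-drug values to be less variable than placebo, and no passage says so. It also has nobody off drug, so it does not use the mechanism described.

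Third, a shared matrix is the conventional reading, the SAP text specifies no interval for the primary effect, and the half-width changes by about 0.6 points (8.17 − 7.54) on a 40-point effect. These points keep the matter minor. They do not remove it, because the standard error still has to be right for whatever is reported.

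Fourth, SAP 9.6 could be said to cover unequal variances. It names no method and leaves the choice until after the assumptions are checked. The Quade test gives no interval for the mean difference.

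Fifth, the by-arm interval is slightly worse when stoppers are partly unobserved, because it is narrower around a biased estimate. That is correct and belongs among the costs.

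**Conclusion.** The point holds as a minor, cheap improvement. Under the natural reading of SAP 10.5.1.1, the week 24 standard error is right only when the arm variances are equal, and keeping off-drug values in the analysis gives no reason to expect that. If 20 is the within-state SD and stoppers are observed and fully back to baseline, the standard error is about 3% too large at 5% off drug and at most 8.5% too large at 20%. The error is zero if both total SDs are 20.

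A reader might go further and infer that the superiority test is compromised. The documents do not support that. Power is close to 100% in every case examined. With no drug effect there is nothing to lose on stopping, and with equal SDs the type I error is 5.0%. Inflated rates can be produced by assuming a more variable placebo arm (6.8% at SDs of 20 for evolocumab and 25 for placebo), but the documents give no arm-specific SDs. No numerical claim is made for the secondary endpoints.

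**What to change.** Add to SAP 10.5.1.1: *The unstructured covariance will be estimated separately for each randomized treatment group, with Kenward-Roger degrees of freedom. If this model does not converge, a common unstructured matrix with empirical (robust) standard errors and between-within degrees of freedom will be used.* In complete-data simulations the robust fallback covered 94.8% (on-drug SD 20, 20% off drug) and 94.7% (on-drug SD 15, none off drug). SAP 10.5.2 would carry the specification over, since it says "The statistical model and testing of the secondary efficacy endpoints will be similar to the primary analysis of the primary endpoint".

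The cost is one SAP sentence and one model option. Three post-baseline lipid visits (weeks 12, 22 and 24, SAP Appendix A) need 3 × 4/2 = 6 covariance parameters shared, or 12 by arm, with a small loss of degrees of freedom at 150 subjects.

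When week 24 data are missing, the choice also moves the point estimate slightly. In a two-visit check (weeks 12 and 24, assumed correlation 0.6, 20% stopping, half of them missing at week 24) the two estimates differed by 0.0 to 0.1 points on average, and by at most 0.1 to 0.4 points in 95% of trials. Both averaged 33.0 to 35.4 against a true 32. The change therefore does not repair missing-data bias, which must be handled separately.
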